Aim 2. Aim 2A: To examine whether the reduction in drinking in treatment responders (defined as ≥60% reduction during weeks 9-12) is maintained in a 12-week, phase 2 extension of the initial treatment condition (pbo or dutasteride). This will help to determine the clinical utility of dutasteride as a treatment for AUD, which is a chronic, relapsing disorder. Aim 2B: Increase the number of dutasteride double-blind treated subjects by including in the 12-week phase 2 a cross-over for pbo non-responders to dutasteride and for dutasteride non-responders to naltrexone, a medication with a different mechanism of action compared with dutasteride.

We hypothesize that reductions in drinking for dutasteride responders in phase 1 will be maintained during the 12-week extension period. Additionally, we hypothesize that phase 1 non-responders on pbo will have significant reductions in drinking when crossed over to dutasteride in the second 12-week phase. Further, we expect that a portion of dutasteride non-responders will have significant reductions in drinking when treated with naltrexone, consistent with models of individual genetic and environmental factors producing differences in individual subject responses to medications with different mechanisms of action.

Aim 3. To examine baseline measures of drinking to cope, trait anxiety, perceived life stress, or early life adversity predict dutasteride treatment efficacy, and secondarily, whether a common genetic variation, rs1360780, in the *FKBP5* gene, which encodes a modulator of the intra-cellular steroid hormone signaling system and HPA stress response system, moderates dutasteride treatment response as an interactive effect with these negative affect/life stress measures. We hypothesize that dutasteride treatment benefits

relative to placebo will be greatest for subjects reporting more drinking to cope, greater anxiety, perceived stress or a history of trauma/adversity, particularly for those who are carriers of the *FKBP5* rs1360780 T-allele.

Section 2. RESEARCH STRATEGY

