Drinking outcomes. Comparison of treatment groups for the modified intention to treat sample (N=135) on the primary outcomes of HDD/week and drinks/ week using generalized linear mixed models (GLMM) showed significant treatment x time interactions (HDD F=9.2; df=1,1406, p=0.002 and SD/wk F=4.8, df=1,1406, p= 0.028). While a minority of our subjects smoke, in view of prior reports of differential medication effects among smokers vs. non-smokers for naltrexone we examined GLMM models that included smoking status, treatment condition, treatment x time, and treatment x smoking as predictors, and identified significant 2-way interactions of treatment x time (F=9.1, df=1,1404, p=0.003 and F=4.4, df=1,1403, p=0.035 for HDD and SD/wk, respectively), and treatment x smoking (F=8.4, df=1,1404, p=0.004 and F=10.9, df=1,1403, p=0.001 for HDD and SD/wk, respectively), such that smokers (n=12) treated with dutasteride drank more throughout the treatment period than smokers treated with pbo (n=12), while the opposite response was observed for non-smokers (dutasteride=56; pbo=55). Smokers and nonsmokers did not differ on baseline drinking, age, Spielberger State Anxiety (SAI) or Beck Depression Inventory (BDI) scores. The interaction of drug x smoking status may relate to the induction by tobacco of phase I metabolism cytochrome P450 and aldo-keto reductase enzymes (Nagaraj, Beckers et al. 2006), the latter of which are involved in neuroactive steroid biosynthesis and metabolism. A prior study showed a positive correlation between serum cotinine levels and the neuroactive steroid allopregnanolone in a sample of 28 men (Marx, Trost et al. 2006). Somewhat surprisingly, with limited exceptions (Fucito, Park et al. 2012, Litten, Ryan et al. 2013, Schacht, Randall et al. 2017) reports for recent RCTs for AUD either did not report the proportion of smokers (Johnson, Ait-Daoud et al. 2003, Johnson, Rosenthal et al. 2007, Johnson, Ait-Daoud et al. 2011, Johnson, Seneviratne et al. 2013, Kranzler, [name] et al. 2014) or did not include smoking status in the analysis of outcomes (Anton, O'Malley et al. 2006, Anton, Myrick et al. 2011, Fertig, Ryan et al. 2012, Litten, Fertig et al. 2012). Interestingly, in the reports by Fucito et al. (Fucito, Park et al. 2012) and Schacht et al. (Schacht, Randall et al. 2017) naltrexone only benefited drinkers who also smoked while our results with dutasteride indicated only non-smokers were responsive, presumably reflecting distinct mechanisms of change. We will include smokers in the proposed study to further evaluate our initial findings. Dutasteride nonresponsive smokers in phase 1 may experience treatment responsive to naltrexone in phase 2 of the proposed study which would support use of smoking as a factor in individualized treatment recommendations.

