dutasteride arm non-responders switched to naltrexone to determine whether naltrexone is effective in reducing drinking in dutasteride non-responders. An interrupted time series regression using mixed models will be used (Wagner, Soumerai et al. 2002, mallinckrodt and Lipkovich 2017), where in addition to a variable for week an indicator variable for phase, a second weekly variable that is sequentially coded beginning at phase 2 and the interaction of the two variables will be included in the model. The phase indicator variable will measure change when entering phase 2 and the second weekly variable will measure change in trajectory deviating from phase 1. In addition, a restricted period analysis focusing on the average of the last 4 weeks of phase 1 compared to average of the last 4 weeks of phase 2 will be conducted. This may be more sensitive if the first few weeks of each phase show limited initial response, which would dilute the effects for phase and the interaction for the interrupted regression model. For the first group, dutasteride responders, a non-inferiority test will be used where the non-inferior margin will be 20% above the drinking levels during phase 1. For the latter two groups of non-responders a superiority test will be used.

For aim 3, analysis of drinking outcomes will be repeated including baseline measures of DTC, trait anxiety, perceived stress, adverse child event count and genotype for the *FKBP5* rs1360780 SNP (CC vs. T-carrier) as additional between-subject factors together with the 2- and 3-way interactions of medication condition with DTC, SAI, PSS or ACES measures and *FKBP5* genotype. We will include both Blacks and Caucasians in the pharmacogenetics analysis as our prior study showed similar interactions of *FKBP5* genotype with life stress on drinking measures in both Black and Caucasian college students (Lieberman, Armeli et al. 2016).

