2.C.9.b. Sample size considerations: For Aim 1, the proposed sample size of 160 completing the phase 1 12-week treatment (80 per arm), has 80% power to show statistical significance (α =0.05) for medium-size effects, d=0.4, such as observed in our initial RCT of dutasteride in men (d=0.38 for change in SDs/wk from baseline to last month of treatment comparing dutasteride and pbo n=91]. For Aim 2a, assuming 80% power and α =0.05 and a sample of 40 responder subjects continuing on dutasteride, the non-inferior margin limit would be an increase of 0.67 HDD/wk or 5 SDs/wk during the second 12 weeks dutasteride treatment. For Aim 2b, a sample of 64 placebo non-responders crossing over to dutasteride for phase 2 would have 90% power to detect a medium effect size for reduction in drinking in phase 2 using a within-subjects t-test. For Aim 3, using the GLMPOWER procedure and the between cell effects for the preliminary data presented above (section 2.B.2) for the 2-way interaction of drinking to cope x drug, a sample of 160 subjects in phase 1 would have 80% power to detect the magnitude of this interaction seen in the preliminary dataset.

Table 3. Timeline for recruitment and other study objectives:

Dutasteride AUD#2 protocok V9 (05-18-2022)

IRB NUMBER: 19-147-2 IRB APPROVAL DATE: 02/27/2024

Staff training & study prep										
Patient enrollment & randomizing 5/mo										
3- and 6-month follow-up										
Data entry & cleaning										
Data analysis & Report writing										

Section 3. PROTECTION OF HUMAN SUBJECTS

3.A Risks to Human Subjects

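### The Aim 3 model names trait anxiety as a main effect but SAI, elsewhere spelled out as state anxiety, in the treatment interactions, and does not say whether the moderator scores are continuous or cut

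*Combined protocol and SAP*

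**What the plan says.** The Specific Aims state Aim 3 as: "To examine baseline measures of drinking to cope, trait anxiety, perceived life stress, or early life adversity predict dutasteride treatment efficacy". The hypothesis that follows is looser. It expects the largest benefit in subjects "reporting more drinking to cope, greater anxiety, perceived stress or a history of trauma/adversity", with no choice between trait and state anxiety.

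Section 2.C.9.a.2 (Efficacy) repeats the drinking models for Aim 3 "including baseline measures of DTC, trait anxiety, perceived stress, adverse child event count", and FKBP5 genotype, "as additional between-subject factors". The same sentence then adds the moderator terms: "together with the 2- and 3-way interactions of medication condition with DTC, SAI, PSS or ACES measures", and genotype.

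Section 2.B.2 (Preliminary studies) gives the abbreviation as "Spielberger State Anxiety (SAI" when it compares smokers with non-smokers. Later, in the account of possible predictors, it expands SAI as the Spielberger inventory without saying state or trait. Table 1 lists state versus trait anxiety among the moderators. Section 2.C.6.b.3 plans to examine both pre-treatment scores as predictors.

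Section 2.C.9.b claims 80% power at 160 subjects for the drinking-to-cope by drug interaction, using the "between cell effects for the preliminary data".

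**The concern.** Moderation is tested by the interaction with treatment, not by the main effect. If SAI means state anxiety, the model has a main effect for one anxiety score and a treatment interaction for the other. The term that would test trait anxiety as a predictor of efficacy is then absent, and the state interaction stands without its own main effect.

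If both scores are tried, the anxiety moderator has four possible tests over the two primary outcomes (2 scores x 2 outcomes) where one score would give two, and the Aim 3 text gives no rule for choosing. For one outcome, picking the better of two independent tests at 5% has an error rate of 1 - 0.95² = 9.75%.

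The coding of the scores is a separate gap. Cutting a continuous score discards information, and interaction tests have little to spare. If the cut points are not fixed beforehand, they too can be chosen after the data are seen.

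**Working it through.** **1. Which anxiety score is in the interaction?**

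- Aim 3 (Specific Aims): trait anxiety.
- Main-effect list (2.C.9.a.2): drinking to cope (DTC), trait anxiety, perceived stress, adverse-event count, genotype.
- Interaction list (same sentence): DTC, SAI, PSS, ACES, with genotype.
- SAI in 2.B.2: state anxiety at one place, unlabelled at another.
- The last paragraph of 2.B.2 presents the trait measure (STAI) as an addition to what the pilot had. This supports reading the pilot's SAI as state.
- Table 1 and 2.C.6.b.3: both scores, with no lead score. Table 2 schedules trait at screening and state at visit 2.

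Three of the four moderators match across the two lists. Only anxiety does not.

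**2. Are the scores cut?**

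- For: the base model in 2.C.9.a.2 contrasts a factor (medication) with a continuous covariate (week), and the Aim 3 scores are called factors alongside the two-level genotype. The power rests on cells. The pilot displays use median splits.
- Against: no analysis cut point is stated. The only cut for the new trial is DTC at 25%, for urn randomization (2.C.3.d). The adverse-event measure is called a count.

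The coding is therefore undefined, with the wording leaning towards categories.

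**3. Can the 80% be reproduced?** No. The cell means and standard deviation given to the power procedure are not in the documents. As a bracket, scale the pilot interaction F by sample size. The pilot cells are 31 + 25 + 23 + 30 = 109. Assume two-sided 0.05, since the plan does not state sidedness; power = Φ(√(F x 160/109) - 1.96).

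- HDD/wk, F = 10.2: √14.97 = 3.87, power 97%.
- SD/wk, F = 4.9: √7.19 = 2.68, power 76%.

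These lie on either side of 80% and neither confirm nor refute it.

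**4. What does a cut cost?** For a normal score with a linear interaction, a cut that leaves a share p in the high group keeps φ(c)²/[p(1 - p)] of the information, where c is the cut in standard units.

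- Median split: 0.3989²/0.25 = 2/π = 0.637, a loss of 36%.
- The pilot DTC split (53 of 109 high): 0.636.
- 30% high: 0.576. 20% high: 0.490.

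Power of 80% corresponds to a standardised effect of 1.960 + 0.842 = 2.80, and √0.637 = 0.798.

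- If the 80% is for split scores: 2.80/0.798 = 3.51, and Φ(3.51 - 1.96) = 94% with continuous scores. The same 80% would then need about 160 x 0.637 = 102 subjects.
- If the 80% is for a continuous score: 2.80 x 0.798 = 2.24, and Φ(2.24 - 1.96) = 61% with a median split. Getting back to 80% would need about 160/0.637 = 251 subjects.

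A simulation at n = 160 (5,000 runs, slope set for a nominal 80% with a continuous score) gave, for continuous against median split: normal score 77% and 58%; uniform 78% and 65%; skewed (gamma) 76% and 52%. There is a loss in each case, and its size depends on the shape of the score.

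**The case against.** The best defence is that the two lists in 2.C.9.a.2 run in the same order, so SAI may simply be shorthand for the anxiety measure just named. The unlabelled expansion in 2.B.2 allows that reading, and 2.C.6.b.3 plans both scores in any case. This stands as far as intent goes: the text does not prove that the trait test has been dropped. It does not settle which score is in the model.

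Three stronger readings are tempting, and the documents do not support them.

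- *That the Aim 3 hypothesis goes untested.* The hypothesis sentence speaks only of greater anxiety, and the DTC, PSS and ACES interactions are all listed. At most the trait-anxiety part is affected. Nor is a different instrument involved: trait and state are the two 20-item halves of one 40-item STAI.
- *That the scores will be dichotomised.* The plan does not use its terms strictly. It also calls sex and smoking status covariates. The pilot reports an interaction with the DTC score before describing it by a median split, so that test may have been continuous.
- *That power falls from 80% to 61%.* The wording about cells, which is the main evidence for cut scores, implies that the 80% already describes them. On that reading the statement is a gain to about 94%.

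It is also fair to say that which anxiety score leads is the investigators' scientific choice. The plan only has to make that choice explicit.

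**Conclusion.** The point holds in a limited form. On the definition of SAI as state anxiety in 2.B.2, the anxiety term is wrong as written: the medication by trait-anxiety interaction that Aim 3 needs is not specified, and the state interaction has no matching main effect. Because the abbreviation is left unlabelled at another place, this is an unresolved inconsistency in one of four moderators. It is not proof that the trait test was abandoned.

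Using continuous scores is a free improvement. The gain from about 80% to 94%, or the avoided drop from 80% to 61%, depends on which coding the stated power describes. Both figures assume a normal score, a linear interaction and a median cut, none of which the plan states. The 80% concerns DTC only, so these figures are illustrative for anxiety, perceived stress and childhood adversity.

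**What to change.** In the Aim 3 paragraph of 2.C.9.a.2:

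1. Replace SAI with STAI-trait in the interaction list, so that it matches the aim and the main effect.
2. If state anxiety is also examined, as Table 1 and 2.C.6.b.3 suggest, give it its own main effect and interaction, and say in advance which score is the lead test.
3. Enter DTC, STAI, PSS and ACES as continuous covariates with their main effects. Keep high/low groups for display only.
4. In 2.C.9.b, restate the Aim 3 power on that coding and give the inputs.

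The cost is a few words and one power calculation. No new data or visits are needed, and the randomization strata can stay as they are. The change should be dated before unblinding.

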Document title: IRB approved study protocol at time of study initiation

NCT04098302: Dutasteride Treatment for Reducing Heavy Drinking in

AUD: Predictors of Efficacy

Protocol date 05/18/2022

IRB Number: 19-147-2

IRB approval date 2/27/2024

Alcohol Research Center Department of Psychiatry University of Connecticut School of Medicine [name]

Protocol Title: Dutasteride treatment for reducing heavy drinking in AUD: Predictors of efficacy.

Principal Investigator: [name], PhD

Co-investigators: [name]., [name],

Abstract

Heavy drinking remains a significant public health problem and is frequently under treated. Although several medications have been shown to help patients stop or reduce drinking, additional medication options are needed as there is considerable variability in effectiveness or tolerability of existing medications for individual patients. Additionally, identification of individual subject level predictors of efficacy are needed to better personalize pharmacotherapy treatment recommendations. This study will seek to replicate and extend our results showing efficacy of a novel medication dutasteride for reducing drinking and will examine potential easily measured predictors of response.

Dutasteride is a widely prescribed medication for benign prostatic hypertrophy and androgenic hair loss that also modulates the elimination of cortisol and the production of some neuroactive steroids. Changes in the regulation of cortisol and neuroactive steroids have each been suggested as factors which may contribute to the maintenance of alcohol dependence. Data from a recently completed first randomized placebo controlled trial of dutasteride for AUD in a sample of male drinkers, indicates that dutasteride is well tolerated in alcoholics and has efficacy in helping subjects reduce drinking. Additionally, results indicate that dutasteride may be particularly helpful for patients who drink to cope with anxiety and negative emotions, a group of patients with poor response to other treatments.

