The proposed study will extend these results by including both sexes and extend our analysis of the relationship of baseline drinking to cope (DTC) and anxiety by adding baseline standardized questionnaires measuring trait anxiety (STAI), early life adversity (ACES), and a perceived stress scale (PSS) which in other settings was more predictive of health care utilization than stressful life event counts (Cohen, Kamarck et al. 1983). Women are expected to have a greater likelihood of elevated DTC, ACES, trait anxiety scores (Smith and Randall 2012) which will enrich our sample in subjects potentially more responsive to dutasteride vs. pbo. We will use separate randomizations for women vs. men and include dichotomized scores for DTC and *FKBP5* risk allele carrier status in our URN randomization to balance for these potential predictors of efficacy. This study may identify easy to score pre-treatment measures such as the CDMQ, ACES, STAI, PSS and genotype that could be clinically useful for making personalized treatment recommendations regarding use of dutasteride to reduce heavy drinking.

2.C. Experimental Approach / Research Plan

2.C.1. General Design: The study will be conducted in the UCHC Clinical Research Center (CRC) clinic. Random assignment to initial treatment group and double-blind conditions will be maintained throughout the study. The study consists of two 12-week phases (**Table 1**), the first being a 12-week parallel-groups comparison of dutasteride and pbo to evaluate the safety and efficacy of dutasteride 1 mg/day in reducing the likelihood of drinking and heavy drinking in a sample of treatment-seeking men and women with AUD. In the second 12-week phase, responders in phase 1 (defined as a ≥60% reduction in SD/wk for weeks 9-12 compared with screening) will continue on their initial medication assignment, while non-responder subjects treated with placebo will cross over to dutasteride, and non-responder subjects treated with dutasteride will cross over to naltrexone. This design maintains double blind conditions in both phases 1 and 2 and is innovative. This design will: i) promote retention and recruitment, as subjects who do not respond to treatment in phase 1 will cross-over to an active FDA approved medication for AUD, ii) provide two comparisons to examine dutasteride efficacy, a between-subjects

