2.C.9.a.2. Efficacy: Primary treatment outcomes will be defined in terms of HDD/wk and SD/wk based on TLFB reports of drinking. Reduction in these measures is related to health benefits of reduced drinking. These are the measures that are used to define non-hazardous drinking. Secondary outcomes will include proportion of days abstinent (PDA), % of subjects with no HDDs, % of subjects with non-hazardous drinking (no HDD and SD/week <15 men/<8 women) during the last 4 weeks of each treatment phase, and change in PEth at end of each treatment phase relative to baseline.

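### Aim 3 lists at least 18 moderator tests with no declared lead test and no multiplicity rule, so the chance of a false predictor of dutasteride response is well above 5%

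*Combined protocol and SAP*

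**What the plan says.** Section 2.C.9.a.2 (Efficacy) sets two outcomes side by side: "Primary treatment outcomes will be defined in terms of HDD/wk and SD/wk". For Aim 3 it repeats the analysis of drinking outcomes with "baseline measures of DTC, trait anxiety, perceived stress, adverse child event count and genotype" as between-subject factors, together with the "2- and 3-way interactions of medication condition with DTC, SAI, PSS or ACES measures" and FKBP5 genotype.

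Section 2.C.9.b (Sample size considerations) gives one Aim 3 power statement, and its scope is limited to a calculation "for the 2-way interaction of drinking to cope x drug". The claim made there is that "a sample of 160 subjects in phase 1 would have 80% power to detect the magnitude of this interaction seen in the preliminary dataset". It does not say which outcome this refers to, and it gives no alpha for Aim 3. The 0.05 level is stated for Aim 1 ("has 80% power to show statistical significance (α =0.05) for medium-size effects, d=0.4") and for Aim 2a.

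The Specific Aims state a directional Aim 3 hypothesis: benefit over placebo is expected to be greatest with more drinking to cope, anxiety, perceived stress or adversity. The four are offered as alternatives, and none is singled out. The same paragraph calls the genotype question secondary. No section sets a primary interaction, a testing order or an adjustment for Aim 3.

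**The concern.** Aim 3 is more than a post hoc search. The trial is titled "Dutasteride Treatment for Reducing Heavy Drinking in AUD: Predictors of Efficacy", and Aim 3 is a specific aim with its own hypothesis and power statement. Section 2.B.2 says the trial may identify baseline measures that "could be clinically useful for making personalized treatment recommendations". When four alternative moderators, a genotype and two outcomes stand unranked, a nominal hit on any of them in the expected direction can be reported as support.

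The DTC interaction also came out of a search. Section 2.B.2 reports that several baseline measures were examined in the earlier trial, within the 111 non-smokers, and that among them only the DTC score interacted significantly with medication. The new trial's particular value for Aim 3 is an independent replication of that result. Leaving it unranked among 18 tests blurs replication with new searching.

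**Working it through.** **Count.** There are five moderators (DTC, anxiety, perceived stress, adverse child experiences, genotype), so five 2-way terms with medication. Each of the four scores with genotype and medication gives four 3-way terms. (5 + 4) x 2 outcomes = 18. This is a low count. It omits state anxiety as a further predictor (2.C.6.b.3), childhood trauma on the TESI (2.C.6.b.1), sex by treatment, any moderator terms with week, the secondary outcomes and the three analysis sets (2.C.9.a.2).

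**The plan's own figure.** The 80% for DTC by drug cannot be reproduced exactly, because the cell effects entered in GLMPOWER are not given. As an approximation, scale the pilot F by sample size, 160/109, where 109 = 31 + 25 + 23 + 30 from the Figure 2 legend, and use power = Φ(√ncp − 1.960):

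- HDD/wk: ncp = 10.2 x 160/109 = 14.97; Φ(3.869 − 1.960) = 97%.
- SD/wk: ncp = 4.9 x 160/109 = 7.19; Φ(2.682 − 1.960) = 76%.

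The stated 80% lies between the two, so which outcome it refers to matters.

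**False positives, independent tests, no real moderator, 0.05 each.** The formula is 1 − 0.95^k:

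| Family | k | Chance of at least one |
|---|---|---|
| All interactions, both outcomes | 18 | 60% |
| All except DTC, if DTC is real | 16 | 56% |
| All interactions, one outcome | 9 | 37% |
| Four self-report measures, both outcomes | 8 | 34% |

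The expected number of false positives over 18 tests is 18 x 0.05 = 0.9.

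**Allowing for correlation.** The tests are not independent. The protocol gives r = .36 between DTC and anxiety. It gives no other moderator correlations and no correlation between HDD/wk and SD/wk, so these are assumed over a range. The simulation used n = 160, 2,500 replicates (Monte Carlo standard error about 1 percentage point), linear models, and moderators entered separately or jointly:

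| Outcome correlation (assumed) | 18 tests, moderator r = .36 |
|---|---|
| 0.5 | 55% |
| 0.7 | 52% |
| 0.8 | 49-50% |
| 0.9 | 46% |

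Over outcome correlations 0.5-0.9 and moderator correlations 0-0.6, the 18-test figure runs from 42% to 58%. For the four self-report measures on both outcomes (8 tests) it runs from 20% to 32%.

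**Power after adjustment.** Take 80% at two-sided 0.05 as given, so the standardised effect is 1.960 + 0.842 = 2.802:

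- 0.05/4 = 0.0125: Φ(2.802 − 2.498) = 62%.
- 0.05/8 = 0.00625: Φ(2.802 − 2.734) = 53%.
- 0.05/9 = 0.00556: Φ(2.802 − 2.773) = 51%.
- 0.05/18 = 0.00278: Φ(2.802 − 2.991) = 42%; restoring 80% would need about 300 subjects.

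**The case against.** The best defence is that the protocol signals an order. Aim 3 calls genotype secondary, which covers (1 + 4) x 2 = 10 of the 18 tests. Section 2.C.9.b powers only DTC by drug. Section 2.C.3.d balances the randomisation on DTC and genotype but not on anxiety, stress or adversity. A reader might infer from the silence on multiplicity that there is no lead test at all. The text does not support that; what is missing is a declared one. None of these signals is turned into a primary test, an order or a gate, so the gap remains.

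Three other strong readings also go too far.

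- That any nominally significant moderator would support the aim. The hypothesis is directional, so a result in the opposite direction would not. In the stated direction only, the independent figure is 1 − 0.975^18 = 37%. It is about 24-28% at moderator correlations 0.2-0.36 and outcome correlation 0.7, and about 13-15% for the eight self-report tests. A wrong-direction result could still be reported as a predictor, so the two-sided rate remains relevant.
- That DTC is the only moderator with earlier support. Section 2.B.2 also reports a drug effect in the high-anxiety but not the low-anxiety half, on both outcomes. It gives no formal anxiety interaction test, so DTC has the stronger support but not the only support.
- That the measures are destined for treatment recommendations. The protocol's wording on this is tentative.

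**Conclusion.** The concern stands as a gap in the plan: at least 18 moderator tests, no declared lead test and no multiplicity rule. The chance of at least one false predictor is 60% if the tests are independent and about 42-58% if correlated. For the four self-report measures it is 34% and about 20-32%.

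A reader might shorten this to a coin flip. That describes only the full 18-test family, which includes the genotype tests the protocol calls secondary, so it should not be quoted without that condition.

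The figures rest on three assumptions: a per-test level of 0.05, which the protocol does not state for Aim 3; no real moderator in the family counted; and correlations that, apart from r = .36, are not in the documents. The simulation used linear models in place of the planned mixed models. Even the lowest figure is about four times 5%.

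**What to change.** Before unblinding, add a short paragraph to section 2.C.9.a.2:

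1. Declare medication by DTC on one named outcome as the single confirmatory Aim 3 test at 0.05. HDD/wk is a natural candidate because its pilot interaction was stronger (F = 10.2 against 4.9). State in 2.C.9.b which outcome the 80% power refers to.
2. Apply Holm to a stated family of the remaining 2-way tests. Say whether it covers one outcome (four tests) or both (eight, or nine with DTC on the second outcome). Note that anxiety also has pilot support. Name the anxiety score: the Aim 3 text lists trait anxiety as the measure but SAI in the interactions, and section 2.B.2 at one point expands SAI as state anxiety.
3. Label the 3-way genotype tests exploratory, and report them with estimates and confidence intervals.

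This is a cheap improvement: a few sentences, with no added subjects, visits or data. The DTC lead test pays no alpha penalty. The downside falls on the secondary moderators: a test with 80% power at 0.05 has about 62% at the first Holm step with four tests, and about 51-53% with eight or nine. Bonferroni over all 18 would leave about 42%, which is why a declared order is preferable to a blanket correction.
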